6.2 Per Protocol (PP) Analysis Set

PP analysis set is a subset of the FAS, and will consist of all randomised subjects for whom no key protocol violation is documented. The PP analysis set will provide supportive data for the efficacy analyses.

Allocation of subjects to the PP analysis set will be performed before unblinding of the study. A list of all protocol violations will be documented in a separate file.

6.3 Safety Analysis Set

The safety analysis set will consist of all subjects who received at least one dose of study drug. Subjects will be analysed according to the treatment they actually received. The safety analysis set will be the primary analysis set for safety analyses.

6.4 PK Set

The PK set will consist of all subjects in the safety analysis set who has at least one post-dose PK assessment. PK analyses will be performed using the PK set.

6.5 PD Set

The PD set will consist of all subjects in the safety analysis set who has at least one post-dose PD assessment. PD analyses will be performed using the PD set.

7.0 METHODS OF ANALYSES AND PRESENTATIONS

The following sub-sections would be considered for logical presentation of study data.

7.1 Subject Disposition

The number of subjects screened, screen failure, randomised, treated, subjects in each analysis set, on-going status, study completion status, Follow-up details will be summarized. Subjects who discontinued/withdrawn from the study will be summarized with reason and listed by their primary reason. Subject allocation by study site will also be summarized. Inclusion/exclusion criteria evaluation will be listed. The denominator which is used for the percentage calculation will be mentioned in the table footnote. This table will be summarized overall and by treatment group by using all subjects.

7.2 Demographic and Baseline Characteristics

Demographic data and subject characteristics at Baseline will be summarized overall and by treatment group using descriptive summary statistics for FAS. The demographic and Baseline characteristics include age [continuous summary and categorical summary as Age <65 years, Age ≥65 years], gender, race, pregnancy test result. Also Baseline characteristics results of height, weight, BMI will be summarized overall and by treatment group. All demographic and Baseline characteristics will be listed in full.

7.3 Protocol Deviations

A protocol deviation is defined as any intentional or unintentional change to, or noncompliance with, the approved protocol procedures or requirements. Deviations may result in study termination of an investigator or investigational site or discontinue subjects from study. Examples of deviations include, but are not limited to:

- Informed consent violation.
- Inclusion/exclusion criteria not met.
- Study procedures not followed.
- Missed visit.
- Visit outside study window.
- Others like procedural deviations such as incorrect storage of study drug, failure to update the Internal Consent Form (ICF) when new risks become known etc...

Protocol deviation will be identified by the project team prior to database lock. A summary of major protocol deviations will be provided overall and by treatment group. All protocol deviations (Key and Non-Key) will be listed. All randomised subjects will be included in the summary.

7.4 Medical History

All medical history will be coded using the latest version of Medical Dictionary for Regulatory Activities (MedDRA). The incidence of medical history abnormalities will be summarized using descriptive statistics by system organ class (SOC) and preferred term (PT). Subjects are counted only once in each PT and SOC category. Summary table will be sorted in alphabetical order by SOC and in decreasing frequency of PT based on total number of incidence within each SOC. Safety analysis set will be used for the analysis with actual treatment received for the summary. Medical history will also be displayed in patient listing.

7.5 Prior and Concomitant Medication

Concomitant medication is defined as all medications still being taken by a subject at randomisation and which continue to be taken during the study.

Prior medication is defined as all medications taken by a subject within 1 month prior to randomisation into the study.

Prior and Concomitant medications will be classified using the latest version of World Health Organization Drug Dictionary (WHO drug). All prior/concomitant medication will be listed.

7.6 Study Drug Treatment Duration of Exposure and Compliance

Treatment exposure and compliance will be assessed by maintaining adequate study drug dispensing records. Duration of exposure to study medication (weeks) and compliance (%) will be summarized descriptively.

Duration of exposure = (Last treatment date – First treatment date) + 1.

Treatment Compliance = (Number of study drug taken / number of study drug that should have been taken) x 100.

Where, number of study drug taken = sum of (total number of capsule taken since last visit), and number of study drug that should have been taken = (date of last dose – date of first dose + 1).

Descriptive summary statistics will be used to summarize treatment duration of exposure and compliance. Also the compliance will be summarized categorically as number of subjects with a compliance < 80%, between 80% and 120% and > 120%. Safety analysis set will be used for the analysis with actual treatment received and presented by treatment group and overall. All study drug accountability data will be listed.

7.7 Efficacy Endpoints and Analyses

The primary efficacy analysis will be based on both FAS and PP population. Sensitivity analyses with primary efficacy endpoints will be based on FAS population. The secondary efficacy analysis will be analysed in a descriptive summary statistics based on FAS and PP population. Descriptive summary statistics mentioned in section 5.1 will be performed for all data used

within the context of the efficacy analysis models. Summaries will be presented by visit and by treatment group. Comprehensive listings of all data will be presented.

7.7.1 Primary Efficacy Endpoints and Analyses

The objective of the primary efficacy analysis is the evaluation of the performance of Xanamem™ as compared to placebo for the change in the primary efficacy endpoints ADCOMs and ADAS-Cog v14 from Baseline (Week 0) to Week 12/EOT. The two primary efficacy endpoints will be evaluated in an a priori hierarchical fashion, where the results of the ADAS-Cog v14 analysis will only be interpreted as confirmatory if superiority of Xanamem™ over placebo can be shown for the ADCOMs.

7.7.1.1 ADCOMs/ADAS-Cog v14 score

ADCOMs, composite score (0 - 1.97) is derived from ADAS-Cog v14, CDR-SOB, and MMSE. ADAS-Cog v14 score is sum of all 14 items of ADAS-Cog v14. Scoring details for ADCOMs and ADAS-Cog v 14 score are given in Appendix 3.

For analysis of the primary efficacy variables, analysis of covariance (ANCOVA) model will be used to assess the change in ADCOMs/ADAS-Cog v14 score from Baseline (Week 0) to Week 12/EOT. The ANCOVA model will include treatment group as fixed effects and the Baseline value as a covariate.

The primary efficacy hypothesis is:

$$H_0: \mu_P \leq \mu_X$$

$$H_1: \mu_P > \mu_X,$$

where μ_P and μ_X denote the change from Baseline (Week 0) to Week 12/EOT in ADCOMs and ADAS-Cog v14 for the placebo and Xanamem™ treatment groups, respectively. Both tests will be performed at a type I error rate of 0.05 one-sided, with a priori hierarchical handling of multiplicity, based on the least squares means (LS means) for Week 12/EOT. LS means from the ANCOVA will be used to derive 90% and 95% confidence intervals. The primary efficacy analysis will not replace missing Week 12/EOT.

Unless otherwise specified, the ANCOVA will have the following characteristics:

- All subjects in the FAS will be included in the primary efficacy analysis as long as there are both Baseline and valid post-Baseline measurements at Week 12/EOT available.
- The response variable will be the change in ADCOMs score from Baseline (Week 0) to Week 12/EOT visit. Only post-Baseline measurements collected on the EOT will be considered response values.
- The following covariate will be used in the models:
 - Baseline ADCOMs score

- Treatment group
- The following SAS statements will be employed:

```
proc mixed data=xxxx ;
    class <treatment group>;
    model < change ADCOMs score> = <baseline ADCOMs score>
    <treatment group> ;
    lsmeans <treatment group>/ diff cl alpha=0.05;
    lsmeans <treatment group>/ diff cl alpha=0.10;
    ods output lsmean=xxx diffs=xxx;
run;
```

Baseline ADCOMs score, as well as observed and change from Baseline values at post-Baseline visits, will be summarized descriptively.

The analysis described above will be repeated for ADAS-Cog v14. Also analysis will be repeated on PP analysis set for supportive evidence.

Whilst the European Medicines Agency discussion paper⁵ foresees the use of the linear models for sensitivity analyses, complementing different methods of primary analyses, the type and order of analyses in this study – ANCOVA as primary efficacy analysis and placebo-based imputation as sensitivity analysis – are chosen in a different fashion due to the following reasons:

- The development stage this study is associated with, where the primary aim is to explore a possible therapeutic effect of Xanamem™; in conjunction with
- The relatively short study duration, which can be expected to reduce the number of missing values in either treatment group and
- The fact that the primary efficacy variables will only be assessed at Baseline (Week 0) and Week 12/EOT.

Sensitivity analyses aim at assessing the robustness of the primary efficacy analysis. The following four analyses will be performed:

1) An additional ANCOVA, imputing missing Week 12/EOT data based on resampling from the placebo subjects, taking Baseline values into account

Process

- a) Select records from placebo group with non-missing ADCOMs score at Week 12
- b) Select records from Xanamem group with missing ADCOMs score at Week 12

- c) Merge datasets from a) and b)
(Total number of records in merged dataset = number of records in dataset a) * number of records in dataset b))
- d) Using Baseline (placebo) and Baseline (Xanamem), calculate DIFF variable to find record in placebo group which has smallest in difference with Baseline in test group
DIFF = abs (Baseline (Xanamem) – Baseline (placebo))
- e) Calculate RANDNO variable with RANUNI function and select the smallest randno
- f) Select 1 record for each missing case in Xanamem group and impute ADCOMs score at Week 12 based on ADCOMs score at Week 12 in placebo group
- g) Calculate change from Baseline based on imputed ADCOMs score at Week 12 for Xanamem group
- h) Repeat a) to g) for placebo group and combine both datasets with the records from both groups with non-missing ADCOMs score at Week 12.
- i) Run proc ANCOVA specified above

The following SAS statements will be employed:

For Xanamem group:

```

data placebo;
set indata;
if <treatment group> = Placebo and <VISIT> = Week 12 and AVAL <> missing;
rename CHG=CHG_P BASE=BASE_P ID=ID_P AVAL=AVAL_P;
run;

```

```

data test;
set indata;
if <treatment group> = Test and <VISIT> = Week 12 and AVAL = missing;
run;

```

```

proc sql;
create table outdata as
select *from test, placebo ;
quit;

```

```
proc sort data=outdata;  
by id id_p;  
run;
```

```
data outdata1;  
set outdata;  
diff=abs(BASE - BASE_P);  
seed_no=ID * ID_P;  
randno=ranuni(seed_no);  
AVAL = AVAL_P;  
CHG=AVAL - BASE;  
run;
```

```
proc sort data=outdata1 out=outdata2;  
by id diff randno;  
run;
```

```
proc sort data=outdata2 nodupkey;  
by id;  
run;
```

```
data outdata3;  
set outdata2;  
keep ID <treatment group> BASE AVAL CHG;  
run;
```

For placebo group, follow above process and keep the imputed data in *outdata4*.

```
data nomissing;  
set indata;  
if aval ^=missing;  
run;
```

```
data FINAL;  
set outdata3 outdata4 nomissing;  
run;
```

where CHG= Change ADCOMs score from Baseline, BASE=baseline ADCOMs score and AVAL=ADCOMs score at Week 12/EOT.

Run PROC MIXED procedure specified above with FINAL dataset.

2) An additional ANCOVA, adding site as a factor. Sites will be pooled by country if randomized subjects will be less than or equal to 10. The following SAS statements will be employed:

```
proc mixed data=xxxx ;  
    class <treatment group> <site>;  
    model < change ADCOMs score> = <baseline ADCOMs score>  
    <treatment group> <site>;  
    lsmeans <treatment group>/ diff cl alpha=0.05;  
ods output lsmean=xxx diffs=xxx;  
run;
```

3) An additional ANCOVA, imputing missing Week 12/EOT data based on placebo-based multiple imputation with missing not at random (MNAR) assumption.

Process

Missing data at Week 12/EOT will be imputed using a regression model based on placebo-based imputation model. The imputation model will include the Baseline values and Week 12/EOT values. The imputation model for the missing observations in both the Xanamem group and the placebo group will be constructed from the observed data in the placebo group only. Under this approach we assume that patients with missing data in both treatment groups would have outcomes like a patient in the placebo group as soon they become missing. The imputation will be performed for 100 times and imputed datasets will be analysed using an ANCOVA model. Approximately 100 imputed datasets will be created and results from the analysis of each imputed dataset will be combined using Rubin's method.

- The following SAS statements will be employed:

```

proc mi data=xxxx nimpute=100 seed=3489876 out=yyyy;
class < treatment group>;
monotone reg (<ADCOMs score at week 12/EOT>);
mnar model(<ADCOMs score at week 12/EOT> /modelobs=(<treatment
group>='Placebo'));
var <baseline ADCOMs score> < ADCOMs score at week 12/EOT>;
run;

data zzzz;
set yyyy;
<change ADCOMs score> = <ADCOMs score at week 12/EOT> -< baseline
ADCOMs score>;
run;

* For 95% Confidence Interval;
proc mixed data=zzzz;
by _imputation_;
class <treatment group>;
model <change ADCOMs score>=<baseline ADCOMs score> <treatment
group>;
lsmeans <treatment group>/ diff cl alpha=0.05;
ods output lsmeans=aaaa diffs=bbbb;
run;

** LSmeans;
proc mianalyze parms(classvar=full)=aaaa;
class <treatment group>;
modeleffects <treatment group>;
ods output parameterestimates=cccc;
run;

** Differences;

```

```

proc mianalyze parms(classvar=full)=bbbb;
class <treatment group>;
modeleffects <treatment group>;
ods output parameterestimates=dddd;
run;

* For 90% Confidence Interval;
proc mixed data=zzzz;
by _imputation_;
class <treatment group>;
model <change ADCOMs score>=<baseline ADCOMs score> <treatment
group>;
lsmeans <treatment group>/ diff cl alpha=0.10;
ods output lsmeans=aaaa2 diffs=bbbb2;
run;

** Differences;
proc mianalyze parms(classvar=full)=bbbb2;
class <treatment group>;
modeleffects <treatment group>;
ods output parameterestimates=dddd2;
run;

```

The analysis described above will be repeated for ADAS-Cog v14.

4) An additional ANCOVA, imputing missing Week 12/EOT data based on multiple imputation using both the Xanamem and placebo group with the missing at random (MAR) assumption.

Process

Missing data at Week 12/EOT will be imputed using a regression based imputation model. The imputation model will include Treatment Group, Baseline values and Week 12/EOT values. The imputation model for the missing observations in both the Xanamem group and the placebo group will be constructed from the complete-case observed data for patients in both the Xanamem group and the placebo group. Under this approach we assume that patients with

missing data in each treatment group would have outcomes like a complete-case patient in that treatment group, where a complete-case patient is one with no missing values for any of the variables in the imputation model. This is known as the complete-case missing values (CCMV) approach. By study design, all patients will have non-missing data for Baseline and Treatment Group. Therefore Week 12/EOT is the only variable in the imputation model which can possibly have missing values. Since there is only one possible missing data pattern for the ADCOMs analysis, an imputation model based on complete-case patients only (CCMV) is equivalent to an imputation model based on patients with any missing data pattern. For this reason, although CCMV is usually a MNAR approach, for the specific case of the ADCOMs analysis (and ADAS-Cog v14 analysis), it is equivalent to a MAR approach.

The imputation will be performed 100 times and imputed datasets will be analysed using an ANCOVA model. Approximately 100 imputed datasets will be created and results from the analysis of each imputed dataset will be combined using Rubin's method.

- The following SAS statements will be employed:

```
proc mi data=xxxx nimpute=100 seed=3489876 out=yyyy;  
class < treatment group>;  
monotone reg (<ADCOMs score at week 12/EOT>);  
mnr model(<ADCOMs score at week 12/EOT>/modelobs=ccmv);  
var <treatment group> <baseline ADCOMs score> < ADCOMs score at week  
12/EOT>;  
run;  
  
data zzzz;  
set yyyy;  
<change ADCOMs score> = <ADCOMs score at week 12/EOT> – <baseline  
ADCOMs score>;  
run;  
  
* For 95% Confidence Interval;  
proc mixed data=yyyy;  
by _imputation_;  
class <treatment group>;
```

```
model<change ADCOMs score>=<baseline ADCOMs score> <treatment
group>;
lsmeans <treatment group>/ diff cl alpha=0.05;
ods output lsmeans=aaaa diffs=bbbb;
run;
```

```
** LSmeans;
proc mianalyze parms(classvar=full)=aaaa;
class <treatment group>;
modeleffects <treatment group>;
ods output parameterestimates=cccc;
run;
```

```
** Differences;
proc mianalyze parms(classvar=full)=bbbb;
class <treatment group>;
modeleffects <treatment group>;
ods output parameterestimates=dddd;
run;
```

```
* For 90% Confidence Interval;
proc mixed data=yyyy;
by _imputation_ ;
class <treatment group>;
model<change ADCOMs score>=<baseline ADCOMs score> <treatment
group>;
lsmeans <treatment group>/ diff cl alpha=0.1;
ods output lsmeans=aaaa2 diffs=bbbb2;
run;
```

```
** Differences;
proc mianalyze parms(classvar=full)=bbbb2;
```

```
class <treatment group>;  
modeffects <treatment group>;  
ods output parameterestimates=dddd2;  
run;
```

The analysis described above will be repeated for ADAS-Cog v14.

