9 INVESTIGATIONAL PLAN

9.1 Overall Study Design and Plan

9.1.1 Description

This is a Phase II, randomised, multi-centre, double-blind, placebo-controlled proof-of-concept study to assess the safety, tolerability and efficacy of oral Xanamem™ QD in adult subjects with mild dementia due to AD.

It is planned to randomise approximately 174 subjects at approximately 20 study sites in three countries (Australia, UK, and USA), with the aim to enrol 7 to 10 subjects at each study site. Subject enrolment will be competitive but a cap of 20 subjects per study site is to be established to avoid any site effects. In case data quality at one study site is creating concerns, an enrolment stop can also occur at fewer than 20 subjects.

The DSMB will periodically meet for the review of accumulating safety study data and will also be involved in the interim efficacy analysis (see [Section 15.2.4](#) for details).

At the Baseline visit (Week 0), eligible subjects will be randomised on a 1:1 ratio to receive either Xanamem™ administered orally, QD (treatment group) or matching placebo (placebo group). Subjects will return to the study site for the Interim visits (Week 4 and Week 8), EOT (Week 12) and Follow-up (4 weeks post last dose of study drug) visits, at which study assessments, as detailed in [Table 1](#) (Schedule of Assessments), will be performed. For further details on the dosing and treatment of subjects, refer to [Section 10](#).

Ad hoc telephone contact may occur at any time-point throughout the study, if deemed necessary by the investigator/study nurse, or if the subject wishes to report an AE.

Subjects will be interviewed and examined at the study site at each visit, and will complete a variety of questionnaires and routine safety evaluations.

Selected subjects will undergo additional PD sampling at specific visits after providing appropriate informed consent. Subjects who do not provide consent for this optional assessment, will still be eligible for the main study.

The overall study duration for an individual subject will be 17 to 20 weeks, including a screening period of 1 to 4 weeks, a double-blind treatment period of 12 weeks, and a follow-up period of 4 weeks. The total duration of the study is expected to be approximately 2 years (last subject last visit).

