10.2.4 Blinding and Randomisation of Study Treatment(s)

A double-blind design is employed so that both the investigators and the subjects will be unaware of the treatment assignment during the whole study.

After written informed consent is obtained from an eligible subject, a **6-digit subject number** will be assigned to this subject. The first digit will denote the country, followed by the study site number and a subject sequence number. This number will be created and allocated by the IWRS, when the subject first enters the system at Screening. The first subject screened at a study site will be assigned the number 001; the second will be assigned the number 002, and so on. For example, Subject 204001 will be the first subject screened at study Site 04 in Country 2. Subjects will be identified during the whole study only by their assigned subject number.

The randomisation codes will be computer-generated by ICON Biostatistics, and kept by a statistician independent from the project team. A copy will be provided to whomever performs the PK and PD assessments, when the PK and PD data are analysed, as well as to the DSMB. Randomisation codes will be generated in blocks stratified by site to ensure approximate balance between dose schemes (1:1) and balanced per site. Randomisation codes will be assigned sequentially as subjects become eligible for randomisation.

Subjects who are eligible for randomisation will be assigned a unique **3-digit randomisation number** at the Baseline (Week 0) visit by IWRS. This randomisation number identifies which treatment will be allocated to the subject. Subjects who withdraw after randomisation are not to be replaced and their randomisation number will not be re-used.

To ensure blinding, the study drug (Xanamem™ capsules) and the matching placebo have the same shape and size. Subjects will receive one capsule of Xanamem™ or one capsule of matching placebo capsule QD during the double-blind treatment period. Labels on the study drug containers will not identify treatment a subject is randomised to. Traceability of the treatment is ensured by the study drug number.

The **4-digit bottle number** will identify study drug packs and will be detailed on the study drug label.

Dispensing of study drug will be coordinated by IWRS. The system will assign a bottle number corresponding to the randomisation arm.

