15 STATISTICAL EVALUATION

15.1 Sample Size and Power

The sample size calculation is based on ADAS-Cog v14 rather than ADCOMs as prior information on the treatment effect to be anticipated in the ADCOMs scale is very limited. The sample size at a one-sided type I error rate of 5% and a power of 80% for detecting a difference of 2 points in the change from Baseline between the treatment groups is 78 subjects per arm, if the standard deviation of the change from Baseline is 5 points. It is planned to include ADAS-Cog v14 into the confirmatory testing stream by the use of a hierarchical testing procedure, such that no adjustment of the type I error rate is necessary.

As a drop-out rate of approximately 10% is assumed, the number of subjects randomised should be increased to approximately 174 (87 per treatment group).

Regarding NFM, the sample size of 156 subjects (approximately 78 subjects per treatment group) is sufficient to ensure that any untoward effects with a true proportion of at least 3% are observed in at least one subject within a treatment group with a probability of approximately 90%. An untoward effect with a true proportion of 5% or higher will be detected with a probability of > 98% in a sample of 78 subjects.

The study is planned to enrol 7 to 10 subjects at each study site.

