15.2.3.5 Evaluation of Primary Efficacy Variables

For analysis of the primary efficacy variables, an analysis of covariance (ANCOVA) model will be used to assess the change in ADCOMs/ADAS-Cog v14 score from Baseline (Week 0) to Week 12/EOT. Treatment group will be used as fixed effect and the baseline value as a covariate. For both primary efficacy variables, the following hypotheses will be tested:

$$H_0: \mu_P \leq \mu_X \text{ vs. } H_1: \mu_P > \mu_X,$$

where μ_P and μ_X denote the change from Baseline to Week 12/EOT in ADCOMs and ADAS-Cog v14 for the placebo and Xanamem™ treatment groups, respectively. Both tests will be performed at a type I error rate of 0.05 one-sided, with a priori hierarchical handling of multiplicity, as described above, based on the least squares means (LS means) for the change from Baseline to Week 12/EOT. LS means from the ANCOVA will be used to derive 90% and 95% confidence intervals. The primary efficacy analysis will not replace missing Week 12/EOT.

The analysis described above will be repeated on the PP set for supportive evidence.

Sensitivity analyses aim at assessing the robustness of the primary efficacy analysis. The following two analyses will be performed:

- An additional ANCOVA, imputing missing Week 12/EOT data based on resampling from the placebo subjects, taking baseline values into account
- An additional ANCOVA, adding site as a factor. Sites contributing few subjects may be pooled. Any decision on pooling sites will be undertaken before unblinding.

Whilst the European Medicines Agency discussion paper⁴⁰ foresees the use of the linear models for sensitivity analyses, complementing different methods of primary analyses, the type and order of analyses in this study – ANCOVA as primary efficacy analysis and placebo-based imputation as sensitivity analysis – are chosen in a different fashion due to the following reasons:

- The development stage this study is associated with, where the primary aim is to explore a possible therapeutic effect of Xanamem™; in conjunction with
- The relatively short study duration which can be expected to reduce the number of missing values in either treatment group and
- The fact that the primary efficacy variables will only be assessed at Baseline and Week 12/EOT.

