3.4 Randomisation and Blinding

This study is randomised, double-blind, placebo-controlled Phase II proof-of-concept study. There is a well-defined randomisation plan for subject's randomisation and blinding. Detailed randomisation details will be document in the study randomisation plan. The randomisation codes will be computer-generated by ICON Biostatistics, and kept by a statistician independent from the project team. A copy will be provided to whoever performs the PK and PD assessments, when the Pharmacokinetic (PK) and Pharmacodynamic (PD) data are analysed, as well as to the DSMB (Data Safety Monitoring Board). Randomisation codes will be generated in blocks stratified by site to ensure approximate balance between dose schemes (1:1) and balanced per site.

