7.7.2.5 Neuropsychological Test Batteries (NTB) – Executive Domain

Total NTB score is the sum of ‘Total correct response’ of Category Fluency Test (CFT) and ‘Total number of correct words’ of Controlled Oral Word Association – Test (COWAT). Each score (‘Total correct response’ of CFT and ‘Total number of correct word’ of COWAT) will also be analysed. Those results will be analysed for Baseline and last visit including change from Baseline. An exploratory ANCOVA will be performed on the change from Baseline (Week 0) to Week 12/EOT in the NTB total score for comparison between the treatment groups, including treatment group as fixed effect, and the Baseline value as a covariate. In addition to the composite score, the change from Baseline (Week 0) to Week 12/EOT in independent components will be analysed with ANCOVA for COWAT and CFT - total correct responses score. The analysis described for primary efficacy analysis will be used for NTB- executive domain data. Sensitivity analysis with adding sites as covariate will be performed in FAS population. Site will be pooled as same to the primary efficacy endpoint. Scoring details are given in Appendix 3.

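### Randomisation is stratified by site, but the primary ANCOVA omits site without a stated reason, and the only site-adjusted check pools every site of the planned size

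*SAP*

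**What the plan says.** Protocol 10.2.4 makes site the stratification factor: "Randomisation codes will be generated in blocks stratified by site to ensure approximate balance between dose schemes (1:1) and balanced per site". SAP 3.4 repeats this.

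For ADCOMs and ADAS-Cog v14, SAP 7.7.1.1 states: "The ANCOVA model will include treatment group as fixed effects and the Baseline value as a covariate". The SAS code there has the same two terms, and Protocol 15.2.3.5 specifies the same model. Both documents give three reasons for making an ANCOVA without imputation the primary analysis (development stage, short duration, only two assessment times). None of them concerns site.

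Site enters the analysis of the primary endpoints only in sensitivity analysis 2. The protocol's rule is loose: "Sites contributing few subjects may be pooled", with the decision taken before unblinding. The SAP makes it numeric: "Sites will be pooled by country if randomized subjects will be less than or equal to 10". SAP 7.7.2.5 carries that rule to the site-adjusted NTB analysis: "Site will be pooled as same to the primary efficacy endpoint".

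On site size, Protocol 15.1 says: "The study is planned to enrol 7 to 10 subjects at each study site". Protocol 9.1.1 allows larger sites: "Subject enrolment will be competitive but a cap of 20 subjects per study site is to be established to avoid any site effects".

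**The concern.** Blocking within site keeps the arms nearly balanced at each site, so differences between sites largely cancel out of the treatment comparison. A model without site still counts those differences as residual noise. Its standard error is then too large and the one-sided 5% test rejects less often than 5% under the null. What is at stake is precision, not bias or false positives.

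The second part concerns the check itself. A sensitivity analysis described as adding site should show whether the result holds up after adjustment for site. With a threshold that covers the whole planned range of site sizes, any site that enrols as planned loses its own level. Agreement between this analysis and the primary one would then say little about site. The cap on enrolment is justified in the protocol by a wish to avoid site effects, so the sponsor regarded them as possible. The cap limits enrolment; it is not a reason to leave the stratification factor out of the model.

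**Working it through.** **Plan's own figure.** Inputs from Protocol 15.1: difference 2, SD of change 5, one-sided alpha 0.05, power 80%. The noncentrality is 2/(5 × √(2/78)) = 2.498, so power at 78 per arm is Φ(2.498 − 1.645) = 80.3%. With 10% dropout, 78/0.9 rounds up to 87 per arm, 174 in total. The plan's 78 and 174 are reproduced.

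**Site size against the threshold.** 174 subjects over 20 sites is 8.7 per site. The range 7 to 10 lies wholly at or below 10. If all sites enrol as planned, the site factor has three levels, the countries. Only sites with 11 to 20 subjects keep their own level.

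**Closed form.** Let ρ be the share of the variance of change that lies between sites. It is not in the documents; 0 to 15% is assumed. With balance within site:

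- ratio of model SE to true SE = 1/√(1 − ρ)
- actual one-sided alpha = 1 − Φ(1.645/√(1 − ρ))
- power without site = Φ((2.498 − 1.645)/√(1 − ρ))
- power with site = Φ(2.498/√(1 − ρ) − 1.645)

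| ρ | SE overstated by | Actual alpha | Power without site | Power with site |
|---|---|---|---|---|
| 5% | 2.6% | 0.046 | 80.9% | 82.1% |
| 10% | 5.4% | 0.041 | 81.6% | 83.8% |
| 15% | 8.5% | 0.037 | 82.3% | 85.6% |

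This ignores lost degrees of freedom and the imbalance that dropout causes, so it overstates the gain.

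**Simulation.** 12,000 trials per setting (Monte Carlo error about 0.4 points): 174 randomised at 20 sites in three countries (7/6/7 assumed), cap 20, blocks of 4 assumed, 10% dropout, true difference 2, total SD 5, no between-country variance. Three layouts were used:

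- (a) every site at 8 or 9
- (b) competitive enrolment with equal site rates, about 37% of subjects in sites above 10
- (c) uneven rates (CV 0.5), about 53% of subjects in sites above 10

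Power (%) for no site / SAP pooling / full site:

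| ρ | (a) | (b) | (c) |
|---|---|---|---|
| 0% | 80.3 / 80.2 / 79.6 | 79.9 / 79.8 / 79.0 | 79.5 / 79.1 / 78.4 |
| 5% | 81.3 / 81.2 / 81.4 | 80.6 / 80.9 / 80.9 | 80.8 / 81.3 / 80.9 |
| 10% | 80.5 / 80.7 / 82.1 | 81.3 / 82.1 / 82.4 | 81.1 / 82.1 / 82.2 |
| 15% | 81.2 / 81.6 / 84.0 | 82.4 / 83.7 / 84.9 | 81.7 / 83.7 / 84.3 |

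Full site adjustment against none:

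- 0%: loses 0.7, 0.9 and 1.1 points
- 5%: gains 0.1, 0.3 and 0.1
- 10%: gains 1.6, 1.1 and 1.1
- 15%: gains 2.8, 2.5 and 2.6

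At 15%, the share of the gain that SAP pooling recovers is 0.4/2.8 = 14% in (a), 1.3/2.5 = 52% in (b) and 2.0/2.6 = 77% in (c). These ratios are rough, given the Monte Carlo error.

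**Second simulation**, with site sizes drawn from 7 to 10 and 3,000 runs for power (error about 0.7 points): at ρ = 10%, power was 79.9 / 80.1 / 81.5 in the same order; at ρ = 20%, 82.1 / 82.6 / 85.9. The null rejection rate at 20% (6,000 runs, error about 0.003) was 0.035 without site, 0.037 with SAP pooling and 0.050 with full site. At planned site sizes, analysis 2 nearly repeats the primary model.

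**The case against.** The strongest reply is that nothing here threatens validity. There is no bias and no inflation of type I error, and simulated power without site stays between 79.5% and 82.4% in every setting, against a planned 80%. A gain needs a site share of 10% or more, and no document gives one. The power figures are for ADAS-Cog v14. ADCOMs is tested first and has no stated SD or effect, so for it only the SE ratio applies. All of this stands and limits the point to one of precision.

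The 7-to-10 figure is an aim, and competitive enrolment up to 20 will probably leave some sites above 10. Layouts (b) and (c) show that pooling then recovers much of the gain, and more still if part of the site variance lies between countries (about 58%, 77% and 89% in the three layouts at 15% when half of it does). This stands too: full collapse to country follows from the plan as written but is not certain.

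Site adjustment is already prespecified as a sensitivity analysis with a numeric rule. That is true, but the rule is what weakens it.

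Finally, the same ANCOVA is reused elsewhere, including the interim at about 50 completers, or about 2.5 per site. An unpooled site factor there would cut residual degrees of freedom from 47 to about 30 and raise the SE by about 11% if sites do not differ, and by about 3% even at a 15% share. This is a fair warning against an unpooled factor. Pooling of small sites deals with it, provided the rule is applied to the counts at that analysis.

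**Conclusion.** The concern holds on the text: site stratifies randomisation, the primary model omits it with no reason given, and the pooling threshold takes in every site of planned size. The consequence is modest and lies on the conservative side. At an assumed site share of 10 to 15%, the primary analysis forgoes about 1 to 2.8 points of power; at 5% the difference is negligible. If sites do not differ, omitting site is better by about 1 point (1.6 in a more uneven layout, 78.0% against 76.4%, so allow up to 2). These figures rest on the assumed site share, blocks of 4 and the assumed site layouts.

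The weakness of the check is clearer than the loss of power. How far analysis 2 examines site depends on how many sites exceed 10, which the documents do not report. This is an improvement worth making, not an error that invalidates the analysis.

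**What to change.** Add site to the primary ANCOVA for ADCOMs and ADAS-Cog v14. Pool within country only those sites too small to contribute a within-site comparison, with the cut-off fixed before unblinding, and keep the no-site model as the sensitivity analysis. The exact cut-off matters little: in layouts (b) and (c), pooling only sites below 4 changed power by at most 0.3 points against no pooling. State that the rule uses the counts at the analysis concerned, so that any interim analysis still to be run is covered.

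If the primary model is kept, state why site is omitted and set the threshold below the planned site size, for both analysis 2 and the NTB analysis. Either way, list the resulting pools before unblinding. The numeric rule entered the SAP on 19 February 2019, the month planned for the last subject's last visit, so site counts should be available.

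The code for analysis 2 requests only 95% limits. Add the 90% limits, which match the one-sided 0.05 test and which the primary code already requests.

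The cost is one CLASS/MODEL term and wording. The wording covers the protocol synopsis and 15.2.3.5, SAP 7.7.1.1 with the analyses that reuse its model, and SAP 10, which at present lists no changes from the protocol. The statistical cost is up to about 19 degrees of freedom, and about 1 point of power (allow up to 2 with uneven sites) if sites do not differ.
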